Evaluation: Patients will be evaluated for set parameters at baseline, one month after completion of primary treatment, six month and one year after completion of cancer treatment. There will be no blinding of any kind. The patients will be kept on recall

for longer period to study effect on the oral health parameters but this will not be part of the present study.

Sample size: Present study will be a prospective randomized parallel group study with allocation ratio of 1:1. As there is no previously available data on frequency of fluoride application as proposed by us. We assume that fluoride monthly application will result in 60 % reduction in decay and quarterly application will result in 30 % reduction in decay at end of 1 year observation period. New patients with established diagnosis of oral cancer will be enrolled as per protocol. Sample of 60 patients in each group (intervention and control) is planned at 1% alpha and 90% power 95% confidence interval.

Sample size calculation:

$$n = \{Z_{1-\alpha/2} \sqrt{P_1(1-P_1)} + Z_{1-\beta} \sqrt{P_2(1-P_2)}\}^2 / (P_1-P_2)^2$$

$$n = 54$$

We assume that monthly professional monthly fluoride application with standard oral care protocol will improve oral health and quality of life parameters by 60 % and Four monthly professional fluoride standard oral care protocol will improve oral health and quality of life parameters 30 % at one year after completion of the study. We will be considering taking 20% as attrition rate (20% of 54 = 10.8, rounded to 11);

The final sample size will be 66patients per group. (Subdivided in 33 patients in gel and varnish group)

The annual load of oral cancer reported at CRI SRHU is approximately 200. We will be randomly recruiting 66 cases in both groups. Each group will be further divided into two subgroups to receive either gel or varnish application.

Statistical analysis: The data will be collected and entered in MS excel 2010. Different statistical analysis will be performed using SPSS software version 22. Intention to treat analysis will be used for the analysis of data.

Trial evaluation and follow up:

The data will be evaluated on 6 monthly duration for adherence to set protocol with information to institutional ethical committee board.

Trial stopping rules:

The clinical trial will be stopped for any of the following reasons.

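### 54 per group does not give 90% power at the stated 1% alpha (it gives about 72%), and the printed formula yields 54 at neither 1% nor 5%

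*Protocol*

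**What the plan says.** Everything at issue is in the sample size paragraph of the Protocol, section 3. Methods, Objective 1.

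- Error rates: "Sample of 60 patients in each group (intervention and control) is planned at 1% alpha and 90% power 95% confidence interval".
- Effect: "We assume that fluoride monthly application will result in 60 % reduction in decay and quarterly application will result in 30 % reduction in decay" at the end of one year.
- Design: "prospective randomized parallel group study with allocation ratio of 1:1".
- Formula: n equals the square of [Z(1−α/2)·√(P1(1−P1)) + Z(1−β)·√(P2(1−P2))], divided by (P1−P2)², with the result n = 54.
- Attrition: "We will be considering taking 20% as attrition rate", worked as "20% of 54 = 10.8, rounded to 11", followed by "The final sample size will be 66patients per group".

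The protocol gives no alpha anywhere else. Its statistical analysis paragraph names only the software and the intention-to-treat principle.

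**The concern.** Three things do not fit together.

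1. One sentence implies two significance thresholds: 1% from the alpha and 5% from the 95% confidence interval.
2. The printed formula uses P1(1−P1) in one term and P2(1−P2) in the other. That is the form for comparing one sample with a fixed value. Comparing two randomised groups needs the variance of both groups in each term.
3. The result, 54, looks too small for 60% versus 30% at 1% alpha and 90% power.

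If so, the power claimed at the stated threshold is wrong, and the protocol does not say which threshold decides the trial. A p-value of 0.03 would be positive on one reading and negative on the other. The trial is unblinded, so the threshold should not be left to be settled once data are in view.

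**Working it through.** **Inputs (all from the sample size paragraph).** P1 = 0.60, P2 = 0.30, difference 0.30, allocation 1:1, power 90% (z = 1.282). The test is two-sided because the formula uses Z(1−α/2), so z = 2.576 at 1% and 1.960 at 5%. P1(1−P1) = 0.24, P2(1−P2) = 0.21, and the mean proportion is 0.45.

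**Step 1: the printed formula, taken literally.**

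- At 1%: (2.576·√0.24 + 1.282·√0.21)² / 0.09 = 37.99, so 38.
- At 5%: (1.960·√0.24 + 1.282·√0.21)² / 0.09 = 26.61, so 27.

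Swapping P1 and P2 gives 37 and 26. The plan's 54 is not reproduced at either level. It does equal 2 × 27, the printed formula's 5% answer doubled.

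**Step 2: two-sample formulas, 90% power.**

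Pooled: n = [z(1−α/2)·√(2·0.45·0.55) + z(1−β)·√(0.24+0.21)]² / 0.30²

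Unpooled: n = [z(1−α/2) + z(1−β)]²·(0.24+0.21) / 0.30²

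| Two-sided alpha | Pooled | Unpooled |
|---|---|---|
| 1% | 79.33, so 80 | 74.40, so 75 |
| 5% | 55.68, so 56 | 52.54, so 53 |

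At 1% the arcsine formula also gives 80, and the continuity-corrected formula gives 86. Only the 5% row comes near 54.

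**Step 3: power of the numbers in the plan.**

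Pooled approximation: power = Φ{[0.30·√n − z(1−α/2)·√0.495] / √0.45}

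For n = 54 at 1%: (2.2045 − 1.8123)/0.6708 = 0.585, and Φ(0.585) = 0.721.
For n = 54 at 5%: (2.2045 − 1.3790)/0.6708 = 1.231, and Φ(1.231) = 0.891.

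| Evaluable per group | Source | Power at 1% | Power at 5% |
|---|---|---|---|
| 52 | 66 × 0.8 = 52.8, rounded down | 70.0% | 87.9% |
| 54 | stated result | 72.1% | 89.1% |
| 60 | sentence stating alpha and power | 77.7% | 92.1% |
| 66 | final size, no losses | 82.4% | 94.3% |

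**Step 4: sensitivity to the test, n = 54.**

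| Method | 1% | 5% |
|---|---|---|
| Pooled normal | 72.1% | 89.1% |
| Unpooled normal | 76.1% | 90.8% |
| Pearson test, exact enumeration | 71.7% | 88.1% |
| Fisher's exact test | 64.8% | 83.9% |

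At two-sided 1% no method reaches 90%, even with all 66 per group retained: the highest figure is 85.5% (unpooled).

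**The case against.** The best counter-argument is that 1% is a slip. The same sentence gives a 95% confidence interval, and 54 lies between the 5% answers of 53 and 56. On that reading the sample is about right and the 72% describes a design nobody intended. This is probably how 54 arose, and it decides which repair is easiest. It does not make the text correct: the protocol says 1%, and its formula fails at 5% as well.

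The directional alternative hypothesis might suggest a one-sided test. The formula uses α/2, and even at one-sided 1% the need is 70 per group (66 unpooled), with 54 giving 80% (83% unpooled).

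The quoted sentence attaches the error rates to 60 patients, not 54. That is true, but 60 gives only 78% pooled or 81% unpooled at 1%.

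A SAP that is not at hand may fix the threshold. It may, but the objection here is not to missing detail: the protocol itself states alpha, power, formula and n, and they contradict one another.

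One caveat stands. The 60% and 30% are described as reductions in decay, and later as improvements in oral health and quality of life, whereas the outcome is the DMFT index. Reading them as proportions of patients follows the protocol's own P(1−P) formula, but neither 72% nor 89% is thereby shown to be the power of a comparison of DMFT scores.

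**Conclusion.** The concern holds. On the protocol's own inputs, 54 per group gives about 72% power at two-sided 1% (65% to 76% depending on the test). The type II error is therefore about 28% (24% to 35%) against the claimed 10%. After the assumed attrition, power is about 70%. Keeping 1% and 90% would take 80 evaluable per group (75 unpooled). The printed formula is a one-sample form that gives 38 or 27, and the threshold is stated in two incompatible ways. If 5% was meant, 54 per group gives about 89% and the defect is one of wording. The figures assume a two-sided comparison of two independent proportions, 60% and 30%, with equal groups.

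**What to change.** Before outcome data are seen, rewrite the sentence and the formula.

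- **Threshold.** State one alpha and the matching confidence level. The reading that fits the sample is a two-sided alpha of 5% with a 95% confidence interval, where 54 evaluable patients per group give about 89% power for 60% versus 30% (pooled normal approximation). If 1% is meant, pair it with a 99% interval and state power as about 72%.
- **Formula.** Print the two-sample formula actually used, so that the stated n can be recalculated.
- **Proportions.** Say in one line what patient-level event the 60% and 30% refer to, so that the power statement has a defined endpoint.
- **Numbers per group.** Reconcile 54, 60 and 66. Adding 11 to 54 gives 65, not 66; allowing for 20% loss by division gives 54/0.8 = 67.5, so 68.

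For either restatement of power the cost is protocol wording only. It does not require more patients, though at 1% the sponsor would be accepting a power well below 90%. Keeping both 1% and 90% is a different decision: 80/0.8 = 100 per group (75/0.8, so 94, unpooled) instead of 66. At 100 per group the total of 200 equals the centre's stated annual load of about 200 cases.

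### The protocol gives two per-group sample sizes, 60 and 66; 66 is evidently the operative one, but the attrition step behind it is wrong, at a small cost in power

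*Protocol*

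**What the plan says.** All the figures for the main comparison stand in the Protocol, section 3 (Methods), Objective 1, under Sample size and Sample size calculation.

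- The opening paragraph gives one target: "Sample of 60 patients in each group (intervention and control) is planned at 1% alpha and 90% power 95% confidence interval".
- The assumed effects are that "fluoride monthly application will result in 60 % reduction in decay" and that "quarterly application will result in 30 % reduction in decay at end of 1 year observation period", in a "prospective randomized parallel group study with allocation ratio of 1:1".
- The calculation then returns 54 per group.
- Attrition is added next: "We will be considering taking 20% as attrition rate (20% of 54 = 10.8, rounded to 11".
- The result is a second target: "The final sample size will be 66patients per group", with the note "Subdivided in 33 patients in gel and varnish group".
- The closing paragraph says that 66 cases will be recruited in both groups.

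Under Objective 2, the pilot is sized at 10 patients, described as 15% of the randomised trial's sample size. The protocol does not say how 60 and 66 relate.

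**The concern.** The per-group target tells staff when to stop enrolling, so it should appear once. Here it appears twice with different values, 120 or 132 patients in total, and neither sentence refers to the other. The 60 cannot be the number before attrition, because that is given separately as 54.

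The inflation also uses the wrong base. An attrition rate of 20% applies to the patients randomised, so a group of N ends with 0.8N. The protocol takes 20% of the number it wants to have left, which always gives too small an N. The sum as printed does not even reach the figure called final.

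At stake are whether the stated N delivers the protocol's own evaluable number at its own attrition rate, and how much power is lost if it does not.

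**Working it through.** **Inputs, all from the sample size section:** evaluable number n = 54 per group; attrition d = 0.20; targets 60 and 66 per group; p1 = 0.60 and p2 = 0.30, treated as proportions because the protocol's formula does so; two-sided test, from the α/2 in that formula; power 90%; alpha stated as 1% beside a 95% confidence interval, so both 1% and 5% are shown.

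**1. Reproducing the protocol's figure.** 0.20 × 54 = 10.8, rounded to 11. Then 54 + 11 = 65. The protocol writes 66. One extra patient would allow an even 33/33 split, but that is an inference; the text does not say so. No step from 54 at 20% gives 60.

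**2. Correct inflation.** N = n/(1 − d) = 54/0.8 = 67.5, so 68 per group (136 in total, 34 per cell).

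**3. What each target leaves, and the loss it can absorb (1 − 54/N).**

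| N per group | Left after 20% loss | Largest loss that keeps 54 |
|---|---|---|
| 60 | 48.0 | 10.0% |
| 65 | 52.0 | 16.9% |
| 66 | 52.8 | 18.2% |
| 68 | 54.4 | 20.6% |

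**4. Power.** The pooled two-proportion approximation is

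power = Φ{ [ |p1 − p2|√n − z(1−α/2) √(2p̄(1−p̄)) ] / √(p1(1−p1) + p2(1−p2)) }.

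Here p̄ = 0.45, √(2 × 0.45 × 0.55) = 0.7036 and √(0.24 + 0.21) = 0.6708. For n = 54 at 5%: (0.3 × 7.348 − 1.960 × 0.7036)/0.6708 = 1.231, and Φ(1.231) = 89.1%. In the same way:

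| Evaluable per group | Two-sided 5% | Two-sided 1% |
|---|---|---|
| 54 (protocol's requirement) | 89.1% | 72.1% |
| 52.8 (66 after 20% loss) | 88.4% | 70.8% |
| 48 (60 after 20% loss) | 85.1% | 65.4% |

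The inflation slip therefore costs 89.1 − 88.4 = 0.7 points at 5% and 72.1 − 70.8 = 1.3 points at 1%. Stopping at 60 would cost 4.0 and 6.7 points against 54.

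**5. Which target governs.** 66 is labelled final, comes after the attrition step, equals 33 + 33 and is repeated in the recruitment sentence. It also fits the pilot: 10/66 = 15.2%, whereas 10/60 = 16.7%. The 60 appears once, before the calculation.

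**6. Standing of the 54.** At 90% power and two-sided 5%, the unpooled formula gives 53 and the pooled one 56, so 54 is about right. At the stated 1% they give 75 and 80. The formula exactly as printed gives 27 at 5% and 38 at 1%. So, at the stated power, 54 fits a two-sided 5% alpha and not 1%.

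**The case against.** The strongest reply is that nothing here would mislead the trial. The number marked as final is clear from its context and the stray 60 only needs deleting. The inflation slip is worth about one evaluable patient per group, and the 20% is itself an assumption given without a source, so tolerating 18.2% instead is within its uncertainty. Most of this stands, and it fixes the weight of the point.

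Four stronger readings are tempting, and the document does not support them.

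- A reader might infer that staff face two live stopping points, so that 48 evaluable per group is a realistic outcome. That would require them to ignore the figure labelled final and repeated at recruitment.
- A reader might infer that the attrition error explains why power is below 90%. It does not: at 5% and by the same method, power is already 89.1% with the full 54.
- A reader might take the recruitment sentence, or the pilot's 15%, to mean 66 patients in the whole trial. The sentence giving the final size says per group, so this is loose wording, though it should be tidied.
- A reader might infer from the comparison with 54 that 54 is sound. It is only the protocol's own benchmark here; at the stated 1% alpha it is too small.

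It could also be said that intention-to-treat analysis keeps every patient. But the protocol itself plans for 20% attrition, so its allowance should deliver the number it calculates.

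**Conclusion.** The point holds, with limited weight. The sample size section states two per-group targets, and they must be reduced to one. The attrition step is wrong twice over: the sum gives 65 and not 66, and the right divisor gives 68. As written, 66 leaves about 52.8 per group at 20% loss, short of 54 by 1.2 patients.

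The loss of power from the slip is minor: 0.7 points at two-sided 5%, 1.3 at 1%. The larger figures, 85.1% and 65.4%, apply only if enrolment stopped at 60, which the rest of the section makes unlikely.

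These figures assume the protocol's 60% and 30% as proportions of patients, equal groups, equal loss in each, and the pooled normal approximation. The conflict between the 1% alpha and the 95% confidence interval is a separate and larger problem, and this point does not settle it.

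**What to change.** 1. Delete the sentence's 60 and state one target throughout: 66 per group, 132 in total, 33 in each gel or varnish cell.
2. Replace the attrition sentence. Say either that 66 leaves about 53 evaluable per group at 20% attrition, or that it keeps 54 only up to 18% attrition. If the sponsor would rather guarantee 54 at 20%, then n/(1 − d) gives 68 per group (136 in total, 34 per cell), and every mention of 66 and 33 must change with it.
3. Change the recruitment sentence to say 66 in each group, and say that the pilot's 15% refers to one group.
4. Do not write in a power figure yet. First reconcile the 1% alpha with the 95% confidence interval, then confirm or recalculate 54, then quote power for the evaluable number at the chosen alpha.

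Keeping 66 costs only protocol wording and a slightly less favourable statement of what it delivers. Moving to 68 costs four more patients in total. If 1% is confirmed at 90% power, the base number itself rises, and that cost belongs to the separate alpha problem.

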Keeping this in consideration we propose use of more stringent professional fluoride application regime of once a month for first one year after oral cancer treatment completion and then at 3 monthly lifelong applications. This will be done along home use of fluoride mouthrinse and fluoride toothpaste lifelong. We would be comparing neutral sodium fluoride gel and varnish use at monthly and three monthly frequency

for first year after radiotherapy. We will be analyzing the clinical benefit of using the proposed fluoride type and frequency for our patients. To best of our knowledge there is no such study conducted before.

There is evidence for both fluoride gel and fluoride varnish as professional application in management of radiation decay in oral cancer patients. Fluoride varnish requires more strict post application routine as compared to gel application. While fluoride gel application has practical issues like gag reflex.²³To best of our knowledge there are no randomized trial on which type of fluoride application is better for oral cancer patients. We aim to also analyze these two forms of professional fluoride applications in our population.

Economics also plays a major role in compliance to oral care for our population. We would also be assessing the economical burden oral care puts on overall expenses in cancer treatment.

The present study will attempt standardization of our oral care module and will test its effectiveness through analysis of outcome in terms of dental health indicators and quality of life among oral cancer patients. This will be done by using the observation design and following patients for a period of one year.

The study will be a prospective randomized controlled trial with two parallel groups. Intervention group will receive the monthly professional fluoride application as part of standard oral care protocol module while the control group will get four monthly professional fluoride application as part of oral care protocol module. Impact on

DMFT index will be the evaluation parameter. This will shed light on need and requirement of fluoride in cancer patients.

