We would also be like to assess the burden and natural history of those oral cancer patients reporting to us who might have taken treatments from outside and had not received any standard oral care due to reasons mentioned in the protocol. We will be comparing their findings separately with our two experimental groups. This will help to highlight the importance of having a standard oral care protocol for all patients of oral cancer. Further it will provide us with information about the status of oral health in patients who have not received any preventive and supportive oral care as a part of their cancer treatment.

The objectives of this study are.

1. To compare the impact of two professional fluoride application regime on DMFT index among patients with oral & oro-pharyngeal cancer.
2. To validate, pilot test, document and standardize institutional oral care protocol for all patients of oral & oro-pharyngeal cancer.

2. Hypothesis

H0: There will be no difference in outcome between two professional fluoride application regimes regarding defined parameters in patients of oral & oro-pharyngeal cancer.

H1: Fluoride application regime with monthly professional application will have better outcome as compared to four monthly application in cancer patients regarding defined parameters.

3. Methods:

Objective 1: To compare the impact of two fluoride application regime on DMFT index among oral cancer patients.

Study design: Randomized controlled trial & observation design

After completion of pilot study, validation of institutional oral care protocol this study will start. The study will be a prospective Randomized controlled trial with parallel groups. Intervention group will be receiving monthly professional fluoride application and control group will be receiving four monthly professional fluoride application. Each group will further be divided in to two subgroups with either gel application or varnish application. The groups will be compared for DMFT index to compare the effectiveness of the fluoride application regime at 4 time points (0,1,6,12 months). The study will be conducted at Cancer research institute, Swami Rama Himalayan University, Dehradun (CRI, SRHU). All new cases of oral cancer receiving treatment will be enrolled.

Inclusion criteria:

1. Patient with histopathological diagnosis of squamous cell carcinoma of oral cavity & oro-pharynx.
2. Patient aged 18 years and above
3. More than 10 teeth in oral cavity
3. Gives consent

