Exclusion criteria:

1. Patients with distant metastasis.
2. Previously received any kind cancer treatment.
3. Use of tobacco.

New patients with definitive histopathological diagnosis of oral cancer will be recruited from oncology OPD after taking informed and written consent according to Helsinki declaration. All eligible patients will be informed and explained by the consultant seeing them about the intent of the study and after giving the consent of participation they will be allocated into the group according to the random table chart provided by the biostatistician. (**Centralized randomization** Room no 004 Oncology OPD at CRI)

A designated person in-charge of random allocation will receive the table of random numbers chart and will make envelopes with slips of either Group A (with gel or varnish application) designates as A-G & A-V and Group B (with gel or varnish application) designates as B-G & B-V inside it. We will be using ‘Sequentially Numbered Opaque Sealed Envelopes’ (SNOSE) which will be made in sets of 100 as per the random number chart with each numbered 1 to 100 and so on.

These envelopes will be stored under lock and key under the designated in charge and will be handed over to researcher, who will open the envelope in a the designated sequence only when the participant reports to him. The research at no point will be aware about the random chart allocation and will only be revealed about the patient group at time of first interaction through a sealed envelop (concealment of allocation). The envelope will be opened in front of patient, which would reveal whether the patient is in Group A or Group B. Group A will receive standard oral care protocol with monthly fluoride regime, Group B will receive standard oral care protocol with quarterly fluoride regime. Further each group will be divided in two subgroup one will receive gel and other will receive varnish application. The **CONSORT** scheme will be adopted for conducting the trial. The researcher will not be involved in the randomization process and will only be aware once the allocation of patients to the group is completed.

The PICO criteria is defined as under

1. **Participants:** All new oral cancer cases.
2. **Intervention:** Monthly professional fluoride application with either gel or varnish.
3. **Comparator:** Four monthly professional fluoride application with either gel or varnish.
4. **Outcome variable:** Oral health & quality of life indicators; DMFT index.

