1. As per the recommendation of ethical committee board any patient with any ethical dilemma which would compromised his treatment will be taken out of the trial.

Trial stopping will not affect in any way the level of care the patient will need.

Ethical consideration: The study will be presented to institutional ethical committee of Swami Rama Himalayan University, for review and upon clearance from the committee, study will be started. All patients will be signing written informed consent with a right to stop and withdraw consent at any point of time during the trial.

Any adverse event reported will be duly documented and reported

The study will be registered after the successful clearance of institutional ethical committee with The Clinical Trials Registry- India (CTRI), before starting enrolling

the first patient. In the present study we will be giving the standard of care of fluoride application i.e. 4 monthly to our control group and there is ambiguity whether monthly fluoride professional application given to intervention group will benefit the oral health. In these situation there are no ethical issues. In any rare case of any problem to the patient regarding the study, the trial monitoring committee will address it and decision of ethical committee in this regard will be considered final.

Any reason of withdrawal of patients consent / participation will in no manner effect the level of care and treatment protocol for these patients will remain same

3. Methods:

Objective 2: To validate, pilot test, document and standardize institutional oral care protocol for all patients of oral & oro-pharyngeal cancer.

Type of study: Validation & Pilot.

Duration: Two Months.

After obtaining the ethical clearance and acceptance of protocol by university validating process will start. For validating our oral care protocol, we will be inviting 6 experts from the filed of oncology care including dental experts, radiation oncologist, medical oncologist, surgical oncologist, nursing expert. First draft will be prepared through review of international guidelines. It will then be shared with the

experts for their comments. After necessary revisions a small group discussion moderated by the researcher will be done. After the consensus among the experts necessary changes will be done and the document will be considered valid. Validity will be judged on the set parameters.

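### Harms are captured only when reported, in an open trial whose randomised factor is contact frequency, so recorded events may differ between the monthly and control arms through opportunity to report alone

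*Protocol*

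**What the plan says.** In the Protocol, section 3 (Methods, Objective 1), the Ethical consideration paragraph holds the only sentence on adverse events: "Any adverse event reported will be duly documented and reported". It names no questions, event list or visits at which harms are to be sought.

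The Evaluation paragraph places assessments at baseline and at 1, 6 and 12 months after cancer treatment in both arms, and adds "There will be no blinding of any kind". Adverse events and tolerability are not named among the parameters assessed.

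The arms differ in frequency of application: "Intervention group will be receiving monthly professional fluoride application and control group will be receiving four monthly professional fluoride application". The allocation text instead says "Group B will receive standard oral care protocol with quarterly fluoride regime". These two descriptions of the control schedule need to be reconciled, but the point below is the same under either.

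On oversight, Trial evaluation and follow up says "The data will be evaluated on 6 monthly duration for adherence to set protocol with information to institutional ethical committee board". A separate route covers a problem arising for an individual patient: "the trial monitoring committee will address it and decision of ethical committee in this regard will be considered final".

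**The concern.** When an event counts only if someone reports it, the number recorded depends on how often patients have the chance to report. Here that chance is tied to the randomised factor: a patient on monthly application meets the dental team far more often than a control patient. Brief, minor complaints between control visits may be forgotten, while the same complaints in the monthly arm are still fresh at the next visit. Because the trial is open, neither patient nor recorder is shielded from expectations about the more intensive regimen.

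The trial is meant to inform a standard institutional protocol, and its proposed outcomes include the effect of application frequency. If harms are later tabulated by frequency, a true excess from three to four times as many applications could not be told apart from extra reporting. A statistical analysis plan cannot repair this, since it can only tabulate what was collected.

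**Working it through.** The protocol gives no figure for contacts or ascertainment, so there is none to reproduce. The check counts scheduled contacts and then asks what they imply when true event rates are equal.

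**Inputs from the Protocol**
- The monthly regimen runs "once a month for first one year after oral cancer treatment completion" (Introduction), giving 12 applications.
- Control applications are four-monthly (3 in the year) or quarterly (4 in the year), depending on the paragraph.
- Shared post-treatment evaluations are at months 1, 6 and 12.

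**Assumptions**
- Applications fall at whole months.
- An application and an evaluation in the same month are one visit.
- No other contact captures events.

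**Step 1: distinct contacts (application months together with evaluation months)**
- Monthly arm: months 1 to 12, so 12.
- Control, four-monthly: months 1, 4, 6, 8, 12, so 5.
- Control, quarterly: months 1, 3, 6, 9, 12, so 5.
- Ratio: 12/5 = 2.40 under either reading. Counting baseline: 13/6 = 2.17. Applications alone: 12/3 = 4.0 or 12/4 = 3.0.

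**Step 2: from contacts to captured events**

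Let events occur evenly over the 12 months, and let an event be reported only if a visit follows within a recall window of w months. The share captured is the sum over the gaps before each visit of min(gap, w), divided by 12.

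- Gaps, monthly arm: twelve of 1 month.
- Gaps, control four-monthly: 1, 3, 2, 2, 4.
- Gaps, control quarterly: 1, 2, 3, 3, 3.

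| Recall w (months) | Monthly arm | Control, four-monthly | Control, quarterly | Ratio |
|---|---|---|---|---|
| 0.5 | 6/12 = 0.50 | 2.5/12 = 0.21 | 2.5/12 = 0.21 | 2.40 |
| 1 | 12/12 = 1.00 | 5/12 = 0.42 | 5/12 = 0.42 | 2.40 |
| 2 | 1.00 | 9/12 = 0.75 | 9/12 = 0.75 | 1.33 |
| 3 | 1.00 | 11/12 = 0.92 | 12/12 = 1.00 | 1.09 or 1.00 |
| 4 | 1.00 | 1.00 | 1.00 | 1.00 |

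The distortion is thus largest for short-lived complaints and vanishes for events still remembered after three to four months.

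**Step 3: gel against varnish**

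Each frequency arm of 66 is divided into 33 gel and 33 varnish. Both forms follow the same schedule within an arm, so the contact ratio between forms is 1.

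**Step 4: the same questions at shared visits only**

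With visits at months 1, 6 and 12 in both arms and w = 1, the share captured is 3/12 = 0.25 in each arm, a ratio of 1. Fewer events are caught, but opportunity is equal.

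**The case against.** Several objections have force.

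- **No comparison of harms between arms is planned.** The outcomes are DMFT, oral health and quality of life. That is so, and it lowers the stakes. It does not remove the problem: events will be recorded, and any later table by arm inherits the unequal opportunity.
- **Other contacts will capture events.** These are cancer patients treated at the same centre, and routine oncology visits would narrow the gap. This stands, and makes the step 2 ratios upper figures for each recall window.
- **The quality-of-life and oral health instruments may contain symptom items.** They may. The operational definitions are not in the text available, so this cannot be settled either way. Patient feedback is explicitly recorded only for the 10-patient pilot.

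Four stronger readings are tempting, and the document does not support them.

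- A reader might infer that the harm data are bound to be biased 2.4-fold. That holds only for short recall. A constant chance of a report per contact gives striking contrasts, such as 1 - 0.95^12 = 46% against 1 - 0.95^5 = 23% of patients with at least one report at 5% per contact. But that model ignores the time since the last visit and makes 2.4:1 automatic, and the 5% is not from the protocol.
- A reader might infer that harms will never be reviewed by arm. The text is silent on this rather than excluding it. Allocation is open, a monitoring committee exists, and a table by arm could sit in an analysis plan not shown.
- A reader might extend the concern to gel against varnish. Step 3 shows why that fails.
- A reader might cite the Introduction's remark, "While fluoride gel application has practical issues like gag reflex", as an example of the bias. Gagging happens in front of the operator at each application, so more of it in the monthly arm would mainly reflect exposure, not reporting.

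**Conclusion.** The concern holds as a risk of differential ascertainment between the frequency arms. Its direction would be towards more recorded events with monthly application. Its size ranges from about 2.4-fold for complaints recalled for up to one month, through about 1.3-fold at two months, to about 1 at three to four months, and is smaller if other contacts capture events. These figures rest on the visit count of 12 against 5, even timing of events and equal true rates. The recall windows are assumed, not taken from the protocol.

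On oversight, the supportable statement is that no periodic review of harms by arm is stated: the six-monthly review is described as one of adherence, and the monitoring committee's role is described case by case. The point does not threaten the DMFT comparison. It merits a cheap correction before enrolment, because unequal collection cannot be mended afterwards.

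**What to change.** 1. In the Evaluation paragraph, add one short fixed list of oral symptom and tolerability questions, with the same wording and recall period, asked in all four cells (A-G, A-V, B-G, B-V) at months 1, 6 and 12, and at baseline for reference. State that any comparison of harms between frequency arms rests on those answers.
2. Keep documenting events reported at any time, as now, and note the visit at which each was reported. Report events seen during an application, such as gagging, separately, per application and by gel or varnish.
3. In Trial evaluation and follow up, add a table of harms by arm to the existing six-monthly report, and send it to the ethics committee and the trial monitoring committee.

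The cost is a few minutes per visit and one extra table, with no new visits or staff. Equal questioning removes the difference in opportunity to report. It does not remove any effect of patients knowing their allocation, which should be acknowledged when the results are read.
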